### 7.1.1 Sensitivity Analyses

In a sensitivity analysis for OSI2-14, the assessment of 2 points improvement will be conducted with the baseline score defined as the last score before first dosing, or a lower score within 24 hours of randomization, whichever is lower.

The classification of whether a score can be considered as within 24 hours of randomization will be determined based on the date and time of randomization and score assessment. If there is partial date/time that make it impossible to determine whether the difference is within 24 hours, to be conservative, the score will be considered to be outside the 24-hour window.

Specifically,

- If the date of lower score is missing, it will be categorized as “outside 24 hours”.
- If the date of lower score is not missing, but hour is missing:
  - It will be categorized as “within 24 hours” if the lower score is measured on the same day of randomization.
  - It will be categorized as “outside 24 hours” if the lower score is measured on subsequent day of randomization.
- If both date and hour are not missing, but minute is missing:
  - It will be categorized as “within 24 hours” if lower score is on same day or subsequent day of randomization and hour is earlier than the hour in randomization time.

It will be categorized as “outside 24 hours” if lower score is on subsequent day of randomization and hour is the same or later than the hour in randomization time.

In the ITT population, the first approximately 50 patients were randomized with an allocation ratio of 2:1, the other patients in the ITT population will be randomized with an allocation ratio of 1:1. The switch of allocation ratio was due to an administrative reason and independent of patient characteristics and thus is not expected to cause any confounding bias. In a sensitivity analysis for OSI2-14, the CMH test will be conducted

stratifying by the randomization stratification factors and the period for the allocation ratio to assess robustness of results.

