**Number of Patients (planned):**

Approximately 300 patients will be enrolled overall as follows:

- a. ~50 patients in Protocol version  $\leq 5.0$
- b. The ITT population will include 247 patients that will be enrolled in Protocol Version 6 and will be randomized to selinexor or placebo in a **1:1** ratio

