#### **4.4. Randomization/Stratification**

Randomization will be performed prior to dosing.

Randomization will be stratified based on the following stratification factors and will maintain the 2:1 allocation between treatment arms (selinexor vs placebo) within each of the stratification categories:

- Use of concomitant therapies: an anti-viral (e.g., remdesivir) or an anti-inflammatory (e.g. hydroxychloroquine, biologics targeting e.g., IL-6 or IL-1).

Note: acetaminophen and nonsteroidal anti-inflammatory drugs (NSAIDs) will not constitute anti-inflammatory agents for the purposes of stratification.

- High Risk Comorbidities: Age > 75, BMI > 30, cancer patients on chemotherapy, patients with cardiac (CAD, AMI, CHF) or pulmonary (COPD, emphysema) disease, diabetes, hypertension. Stratification will be based on number of high risk comorbidities: (1 vs  $\geq 2$  vs 0)

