### **5.4 The Proof of Concept Population**

The Proof of Concept (PoC) Population consists of all patients who are randomized in the study with confirmed SARS-CoV2 infection under protocol version 1.0 to 5.0. This is a proof-of-concept cohort and thus will be analyzed separately. Efficacy and safety endpoints will be presented for descriptive purpose. Patients will be analyzed in the treatment arm to which they were treated.

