## 7.1 Analyses of Primary Efficacy Endpoint

The difference in OSI2-14 rates between treatment arms will be calculated with a 95% confidence interval (CI). Comparison between 2 treatment arms will be performed using the Cochran-Mantel-Haenszel (CMH) test stratified by the randomization stratification factors. The CMH estimate of the odds ratio and its 95% CI and the p-value for testing the treatment difference will be reported.

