## 7.2 Analyses of Secondary Efficacy Endpoints

### 7.2.1 Analyses of Key Secondary Efficacy Endpoints

If the primary endpoint, OSI2-14, is significant in ITT population, the following key secondary endpoints in ITT population will be sequentially tested in the order listed below. If any null hypothesis is not rejected in this sequence of tests, formal sequential testing will be stopped and the analyses of any endpoints thereafter will be nominal only.

- Time to clinical improvement (TTCI-2)
- Overall Death rate on Day 28 (DR-28)
- Rate of mechanical ventilation (RMV)
- Time to mechanical ventilation (TTMV)

For binary endpoints (DR-28, RMV), the difference in rates between treatment arms will be calculated with a 95% confidence interval (CI). Comparison between 2 treatment arms will be performed using the Cochran-Mantel-Haenszel (CMH) test stratified by the randomization stratification factors. The CMH estimate of the odds ratio and its 95% CI and the p-value for testing the treatment difference will be reported.

For time to event endpoints (TTCI-2, TTMV), the number and percentage of patients with the corresponding events will be reported. Median event times with 95% CIs will be estimated by Kaplan-Meier (KM) method for each treatment arm. KM curves by treatment arms will be provided.

The following analysis stratified on randomization strata will be performed:

- Log-rank test stratified to compare the event times between treatment arms

- Hazard ratios of treatment effect with 95% CI estimated by Cox proportional hazards model with Efron's method of tie handling

Non-stratified log rank test and Cox proportional hazards model will be performed as sensitivity analyses.

The Kolmogorov-type Supremum test will be conducted to assess the validity of the proportion hazards assumption in all fitted Cox proportional hazards models. If there is evidence for a violation of the proportional hazards assumption, interaction terms between time-dependent terms and treatment variable (selinexor vs. placebo) will be added to assess time-varying treatment effects.

In sensitivity analysis for RMV, analyses will be conducted with patients who ever used one of the respiratory assistances as below:

- Non-invasive positive pressure mechanical ventilation (CPAP/BiPAP)
- High-flow nasal cannula
- Invasive mechanical ventilation
- Extracorporeal membrane oxygenation (ECMO)

For TICI-2, sensitivity analyses will be performed in the same manner as OSI2-14.

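### The allocation ratio for the ITT patients is stated three ways; if SAP 7.1.1 is right, its no-confounding inference fails and the primary CMH test should be stratified by allocation period

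*SAP*

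**What the plan says.** Three places state an allocation ratio that bears on the ITT population.

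- Protocol synopsis, Number of Patients: the 247 ITT patients "will be enrolled in Protocol Version 6 and will be randomized to selinexor or placebo in a" 1:1 ratio. About 50 other patients, enrolled under version 5.0 or earlier, are counted separately.
- Protocol 4.4: stratified randomization "will maintain the 2:1 allocation between treatment arms (selinexor vs placebo) within each of the stratification categories". No period or protocol version limits this.
- SAP 7.1.1, speaking only of ITT patients: "the first approximately 50 patients were randomized with an allocation ratio of 2:1, the other patients in the ITT population will be randomized" 1:1.

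SAP 7.1.1 then says that the switch was administrative and "independent of patient characteristics and thus is not expected to cause any confounding bias".

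For the primary endpoint SAP 7.1 states: "Comparison between 2 treatment arms will be performed using the Cochran-Mantel-Haenszel (CMH) test stratified by the randomization stratification factors". Those factors are concomitant therapy (four levels in SAP 2.1) and number of high-risk comorbidities (three levels); allocation period is not one of them. SAP 7.1.1 adds period to the CMH test as a sensitivity analysis of OSI2-14, and SAP 7.2.1 extends this by reference: "For TICI-2, sensitivity analyses will be performed in the same manner as OSI2-14" (evidently TTCI-2 is meant). For the key secondary time-to-event endpoints, "The following analysis stratified on randomization strata will be performed", which again leaves period out. No analysis of DR-28, RMV or TTMV uses period, and SAP 2.3 does not mention it for the interim odds ratio and p-value.

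SAP 5.4 keeps a separate proof-of-concept population, "all patients who are randomized in the study with confirmed SARS-CoV2 infection under protocol version 1.0 to 5.0", outside the ITT population.

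**The concern.** The first problem needs no assumption: the three ratios are incompatible, and all stand in current, legible text.

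The second arises only if SAP 7.1.1 is right. Period confounds the comparison when it is linked both to arm and to outcome. A change from 2:1 to 1:1 creates the link to arm by design, and an administrative reason does not remove it. The link to outcome depends on whether Day 14 response changed over time within strata. Protocol 3.1 expects standard of care to change during the trial and to differ between regions. It relies on randomization and stratification to limit the effect, and the concomitant-therapy factor does absorb part of it. But the anti-inflammatory level of that factor pools hydroxychloroquine with IL-6 and IL-1 biologics, and neither region nor baseline ordinal score is a stratum.

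At stake are the primary p-value, which opens the key secondary sequence, and the interim odds ratio and p-value, which determine conditional power (CP) and the sample-size decision. Improvement over time biases against selinexor and costs power. Worsening raises the chance of a false claim for selinexor.

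**Working it through.** **The plan's own figure.** The 247 cannot be reproduced, because the rates and alpha behind it are not visible. Two sums fit: 50 + 247 = 297, about 300; and 1.5 × 247 = 370.5, the stated maximum of 371. The first agrees with the synopsis, which places a group of about 50 outside the 247.

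**Expected arm sizes at N=247 under each statement.** Power is for an assumed 50% vs 67.5%, two-sided 5%.

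| Statement | Selinexor / placebo | Power |
|---|---|---|
| Synopsis, 1:1 | 123.5 / 123.5 | 80.2% |
| Protocol 4.4, 2:1 | 164.7 / 82.3 | 75.9% |
| SAP 7.1.1, mixture | 131.8 / 115.2 | 80.0% |

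**Imbalance under the mixture.** Take exactly 50 early patients: 50 × 2/3 = 33.3 on selinexor and 16.7 on placebo. The rest split equally. At N=247 the later 197 add 98.5 per arm, so the early shares are 33.3/131.8 and 16.7/115.2.

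| Analysis | Early share, selinexor | Early share, placebo | Gap (points) |
|---|---|---|---|
| First interim, N=74 | 73.5% | 58.1% | 15.4 |
| Second interim, N=124 | 47.4% | 31.1% | 16.3 |
| Final, N=247 | 25.3% | 14.5% | 10.8 |

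**Bias.** Bias in the rate difference = share gap × drift in response between periods. The documents give no rates by period, so drift is an assumption.

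| Drift (points) | Bias, final | Bias, second interim |
|---|---|---|
| 5 | 0.5 | 0.8 |
| 10 | 1.1 | 1.6 |
| 15 | 1.6 | 2.5 |
| 20 | 2.2 | 3.3 |

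**Analytic check of the error rate.** At 50% response, SE = 0.5 × √(1/131.8 + 1/115.2) = 6.4 points. A 10-point worsening shifts z by 1.08/6.4 = 0.17, and the upper tail beyond 1.96 − 0.17 is 3.7%. For 20 points the shift is 0.34 and the tail 5.3%.

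**Simulation.** 60,000 trials per scenario; 12 strata; permuted blocks of 6 (4:2) for the first 50 patients and of 4 (2:2) afterwards; CMH test with 12 strata and with 24 (period added); one-sided 2.5%. Late placebo response was 50–70% under the null and 40–60% for power. The odds ratio of 2.1 is an assumption; it gives 76–82% power without drift.

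| Drift (points) | False positives for selinexor if response worsens, no period | Power lost if response improves, relative to the test with period |
|---|---|---|
| 5 | 3.0–3.2% | about 1 point |
| 10 | 3.4–3.8% | 3.5–4 points |
| 15 | 4.2–4.5% | 6.5–7.5 points |
| 20 | 4.9–5.5% | 10–12 points |

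With period as a stratum, false positives are 2.4–2.6% throughout.

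**Second interim.** CP = Φ((z/√t − 1.96)/√(1−t)) with t = 124/247, so CP 30% is z = 1.13 and CP 80% is z = 1.81.

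- 15-point improvement, odds ratio 2.1: the chance of CP below 30% is 28–30% without period (27.5% in a separate run) and 21–24% with it.
- 15-point worsening, null true: the chance of CP at or above 30% is 19% without period and 13% with it.

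Futility is non-binding, so these are probabilities of landing in a zone, not of stopping.

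**Cost and control.** With no drift, adding period costs 1.3–1.7 points of power. Other runs, with different assumed stratum sizes and response models, gave 1.1 to 2.7. With a constant ratio, 1:1 or 2:1, a drift of ±20 points gives bias 0.0 and 2.2–2.4% in each tail.

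**The case against.** The SAP already prespecifies the period-stratified CMH test for OSI2-14 and carries it to TTCI-2, so a reader of the final results would see whether period matters. The harm is doubly conditional: SAP 7.1.1 must be right, and response must drift within strata. If evolving care means better care, the bias runs against selinexor; a 10-point improvement gives one-sided false positives of only 1.7–1.8%, below nominal. No passage suggests that outcomes would worsen, although shifts in case mix or region could cause it. SAP 2.2 breaks off after the total of about 300 and Protocol 9.2 is blacked out after 247; either could hold the allocation history. The early patients in SAP 7.1.1 may simply be the proof-of-concept cohort described as ITT. Finally, period gives 24 strata for 124 patients at the second interim. With no drift there, adding it raises the chance of CP below 30% from about 20% to 21–22% and lowers the chance of CP at or above 80% by 2–3 points.

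Much of this stands as a limit on size. It does not remove the point. Hidden text cannot reconcile three visible statements that conflict. A sensitivity analysis does not protect the decision, because the unadjusted p-value opens the key secondary sequence and the imbalance is largest at the interims. The 24-stratum test held its nominal error at the final analysis without pooling of strata.

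**Conclusion.** The concern holds. The contradiction between the synopsis, Protocol 4.4 and SAP 7.1.1 is certain, and the public text does not settle which ratio applied. If the mixture is real, the no-confounding inference does not follow: about 11% of any within-stratum drift becomes bias at the final analysis and about 16% at the second interim. For small drifts this is modest, about 1.1 points of final bias per 10 points of drift. The error and power figures rest on assumed drift, assumed response rates, an assumed odds ratio of 2.1 and exactly 50 early patients. They lean towards the upper end, because the drift in the simulation was not tied to the concomitant-therapy strata, which would absorb some of it. If the ratio was constant, only the textual correction remains.

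**What to change.** Check the randomization records and make the synopsis, Protocol 4.4 and SAP 7.1.1 state one allocation history for the ITT patients.

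If the mixture is confirmed:

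- make the period-stratified CMH test in SAP 7.1.1 the primary analysis, and keep the test without period as the sensitivity analysis;
- add period as a stratum to the key secondary CMH, log-rank and Cox analyses, and to the interim odds ratio and p-value;
- delete the sentence that rules out confounding.

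A prespecified rule for pooling sparse strata would be a sensible addition, especially at the interims and for DR-28, RMV and TTMV if events are few.

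If the ratio was constant, delete the mixed-ratio paragraph from SAP 7.1.1.

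The cost is wording in both documents and no new data. Under the mixture, expect to give up about 1.5 points of power if there is no time trend (1.1 to 2.7 across the simulations). The change should be made before unblinding.

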### 7.1.2 Subgroup Analyses

The following sub-group analyses will be conducted for OSI2-14 and TTCI-2.

- By age ( $\leq 70$  vs.  $> 70$ )
- Among patients with immune compromised, have hypertension, or have pulmonary disease (smoking history or moderate to severe chronic obstructive pulmonary disease [COPD]), cardiac disease
- By baseline use of concomitant therapies
- By high-risk comorbidities (0 vs 1 vs  $\geq 2$ )
- By race.

## 7.2 Analyses of Secondary Efficacy Endpoints

### 7.2.1 Analyses of Key Secondary Efficacy Endpoints

If the primary endpoint, OSI2-14, is significant in ITT population, the following key secondary endpoints in ITT population will be sequentially tested in the order listed below. If any null hypothesis is not rejected in this sequence of tests, formal sequential testing will be stopped and the analyses of any endpoints thereafter will be nominal only.

- Time to clinical improvement (TTCI-2)
- Overall Death rate on Day 28 (DR-28)
- Rate of mechanical ventilation (RMV)
- Time to mechanical ventilation (TTMV)

For binary endpoints (DR-28, RMV), the difference in rates between treatment arms will be calculated with a 95% confidence interval (CI). Comparison between 2 treatment arms will be performed using the Cochran-Mantel-Haenszel (CMH) test stratified by the randomization stratification factors. The CMH estimate of the odds ratio and its 95% CI and the p-value for testing the treatment difference will be reported.

For time to event endpoints (TTCI-2, TTMV), the number and percentage of patients with the corresponding events will be reported. Median event times with 95% CIs will be estimated by Kaplan-Meier (KM) method for each treatment arm. KM curves by treatment arms will be provided.

The following analysis stratified on randomization strata will be performed:

- Log-rank test stratified to compare the event times between treatment arms

- Hazard ratios of treatment effect with 95% CI estimated by Cox proportional hazards model with Efron's method of tie handling

Non-stratified log rank test and Cox proportional hazards model will be performed as sensitivity analyses.

The Kolmogorov-type Supremum test will be conducted to assess the validity of the proportion hazards assumption in all fitted Cox proportional hazards models. If there is evidence for a violation of the proportional hazards assumption, interaction terms between time-dependent terms and treatment variable (selinexor vs. placebo) will be added to assess time-varying treatment effects.

In sensitivity analysis for RMV, analyses will be conducted with patients who ever used one of the respiratory assistances as below:

- Non-invasive positive pressure mechanical ventilation (CPAP/BiPAP)
- High-flow nasal cannula
- Invasive mechanical ventilation
- Extracorporeal membrane oxygenation (ECMO)

For TICI-2, sensitivity analyses will be performed in the same manner as OSI2-14.

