##### 4.1. Inclusion Criteria

Patients are eligible to be included in the study only if they meet all the following criteria:

1. Age  $\geq 18$  years
2. Confirmed laboratory diagnosis of SARS-CoV2 by standard FDA-approved RT-qPCR assay or equivalent FDA-approved testing (local labs) within 7 days of enrollment.
3. Currently hospitalized.
4. Informed consent.
5. Has symptoms of severe COVID-19 as demonstrated by:
  - a. At least one of the following: fever, cough, sore throat, malaise, headache, muscle pain, shortness of breath at rest or with exertion, confusion, or symptoms of severe lower respiratory symptoms including dyspnea at rest or respiratory distress.
  - b. Clinical signs indicative of lower respiratory infection with COVID-19, with at least one of the following: SaO2  $< 92\%$  on room air in last 12 hours or requires  $\geq 4$  LPM oxygen by nasal canula, non-rebreather/Ventimask (or similar device) or high flow nasal canula in order to maintain SaO2  $\geq 92\%$ , PaO2/FiO2  $< 300$  mm/hg. Patients with COPD or chronic lung disease must demonstrate evidence of increased oxygen needs above baseline.
6. Elevated CRP  $> 2 \times$  ULN
7. Concurrent anti-viral and/or anti-inflammatory agents (e.g., biologics, hydroxychloroquine) are permitted. If in the physician's judgement, it is in the best interest of the patient to use anti-viral or anti-inflammatory treatments, these treatments are to be documented in the patient's chart and entered in the electronic case report form.

Note: Patients who may have received plasma convalescent therapy  $> 48$  hours prior to enrollment with no clinical improvement and who still meet criteria for severe COVID-19 may enroll. On study plasma convalescent therapy is not permitted.

Patient who receive plasma convalescent therapy within 48 hours may be permitted to enroll based on discussion with sponsor.

8. Female patients of childbearing potential must have a negative serum pregnancy test at Screening. Female patients of childbearing potential and fertile male patients must use highly effective methods of contraception throughout the study and for 3 months following the last dose of study treatment. Highly effective methods of contraception are listed in Section 8.3.1.

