##### 4.2. Exclusion Criteria

Patients are excluded from the study if any of the following criteria apply:

1. Evidence of critical COVID-19 based on:
  - a. Respiratory failure (defined by endotracheal intubation and mechanical ventilation, oxygen delivered by noninvasive positive pressure ventilation, or clinical diagnosis of respiratory failure in setting of resource limitations)
  - b. Septic shock (defined by investigator assessment or requires vasopressor)
  - c. Multiple organ dysfunction/failure
2. In the opinion of the investigator, unlikely to survive for at least 48 hours from screening
3. Inadequate hematologic parameters as indicated by the following labs:
  - a. Patients with severe neutropenia ( $ANC < 1000 \times 10^9/L$ ) or
  - b. Thrombocytopenia (e.g., platelets  $< 100,000$  per microliter of blood)
4. Inadequate renal and liver function as indicated by the following labs:
  - a. Creatinine clearance (CrCL)  $< 20$  mL/min using the formula of Cockcroft and Gault.
  - b. Aspartate transaminase (AST) or alanine transaminase (ALT)  $> 5$  x upper limit of normal (ULN)
5. Hyponatremia defined as sodium  $< 130$  mEq/L
6. Unable to take oral medication when informed consent is obtained.
7. Patients with a legal guardian or who are incarcerated.
8. Treatment with strong CYP3A inhibitors or inducers. A list of strong CYP3A inhibitors and inducers is provided in [Appendix 3](#).
9. Pregnant and breastfeeding women.

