**Table 1: Study Objectives and Endpoints**

Objectives	Endpoints
Primary Objectives	
Day 14 Ordinal Scale improvement	
Proportion of patients with at least a 2-point improvement (increase) in the Ordinal Scale from time of randomization (baseline) to Day 14. The Ordinal Score is an assessment of the clinical status at the first assessment on each day of hospitalization.
 
The scale is as follows:
 
 
1. Death;
 
2. Hospitalized, on invasive mechanical ventilation or extracorporeal membrane oxygenation (ECMO);
 
3. Hospitalized, on non-invasive ventilation or high flow oxygen devices;
 
4. Hospitalized, requiring supplemental oxygen;
 
5. Hospitalized, not requiring supplemental oxygen - requiring ongoing medical care (COVID-19 related or otherwise);
 
6. Hospitalized, not requiring supplemental oxygen - no longer requires ongoing medical care;
 
7. Not hospitalized, limitation on activities and/or requiring home oxygen;
 
8. Not hospitalized, no limitations on activities.
 

Key Secondary Objectives	
To evaluate improvement in clinical measures across the 2 treatment arms	
 
• Time to an improvement of 2 point using Ordinal Scale (TTCI-2)
 
• Overall Death Rate on Day 28
 
• Rate of mechanical ventilation
 

	
 
• Time to mechanical ventilation
 

Additional Secondary Objectives	

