**Table 6: Efficacy Endpoints and Definitions**

Endpoint	Definition
Primary Endpoint	
Day 14 Ordinal Scale improvement (OSI2-14)	Proportion of patients with at least a 2 points improvement (increase) in the Ordinal Scale by Day 14. Baseline score is defined as the last score measured before first dosing. The improvement is assessed between the baseline score and the latest score on or before Day 14, End of study (EoS) date, or database cut date, whichever occurs first.
Key Secondary Endpoints	
Time to an improvement of 2 points using Ordinal Scale (TTCI-2)	The time from randomization to an improvement of 2 points on the Ordinal Scale. For patients who didn't achieve clinical improvement of 2 points, 
 
If no death event by Day 28, they will be censored on the last contact date, on or before Day 28, EoS date, or database cut date, whichever occurs first.
 
 If they died by Day 28, they will be censored on Day 28.
Overall death rate on Day 28 (DR-28)	Proportion of patients died on or before Day 28.
Rate of mechanical ventilation (RMV)	Proportion of patients who ever used invasive mechanical ventilation or ECMO during the hospital stay.
Time to mechanical ventilation (TTMV)	Time to the first use of mechanical ventilation. For patients who never used mechanical ventilator, the censoring date is defined as the death date or last contact date (if no death), on or before EoS or database cut date, whichever occurs first.

Additional Secondary Endpoints	
Time to recovery (TTR)	Time to improvement from baseline score of 3 to $\geq 4$ or from a baseline score of 4 to $\geq 5$ by Day 28. For patients who didn't achieve recovery, the censoring rule will be the same as that in TTCI-2.
Day 7 Ordinal Scale 2 points improvement (OSI2-7)	Proportion of patients with at least a 2 points improvement (increase) in the Ordinal Scale from baseline to Day 7. The improvement is assessed between the baseline score and the latest score on or before Day 7, End of study (EoS) date, or database cut date, whichever occurs first.
Day 7 Ordinal Scale 1 point improvement (OSI1-7)	Proportion of patients with at least a 1 point improvement (increase) in the Ordinal Scale from baseline to Day 7. The improvement is assessed the same as in OSI2-7.

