### **7.2.2 Analyses of Additional Secondary Endpoints**

For the additional secondary endpoints, binary endpoints and time to event endpoints will be analyzed similarly as for the key secondary endpoints, with the only exception that there will be no hypothesis testing.

For continuous endpoints (length of hospitalization, length of ICU stay, duration of mechanical ventilation), summary statistics by treatment arm will be provided including number of patients, median, mean, standard deviation, minimum, and maximum.

For duration of mechanical ventilation, sensitivity analyses will be performed in the same manner as RMV.

For PaO2:FiO2 and/or oxygenation index over time, only descriptive statistics will be provided.

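### The RMV sensitivity analysis counts any use of high-flow oxygen, yet patients may enter on high flow, so they are events at baseline in both arms

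*SAP*

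**What the plan says.** - **Main endpoint.** SAP Table 6 defines RMV as "Proportion of patients who ever used invasive mechanical ventilation or ECMO during the hospital stay".
- **Sensitivity analysis.** Under SAP 7.2.1, "analyses will be conducted with patients who ever used one of the respiratory assistances as below". Four supports follow: CPAP/BiPAP, "High-flow nasal cannula", invasive ventilation and ECMO. There is no start date, no new-use condition and no allowance for baseline support.
- **Entry.** Protocol 4.1, criterion 5b, accepts patients who need oxygen by "non-rebreather/Ventimask (or similar device) or high flow nasal canula in order to maintain" saturation. Protocol 4.2, criterion 1a, excludes intubated and ventilated patients and those with "oxygen delivered by noninvasive positive pressure ventilation, or clinical diagnosis of respiratory failure in setting of resource limitations". It does not name high flow.
- **Baseline score.** Score 3 is "Hospitalized, on non-invasive ventilation or high flow oxygen devices" (SAP Table 1). Time to recovery is defined partly from a baseline score of 3, so the plan expects such patients.
- **Test.** The CMH test for RMV is stratified by the randomization factors, which are concomitant therapy and number of comorbidities. Baseline oxygen support is not among them.
- **Duration.** SAP 7.2.2 adds: "For duration of mechanical ventilation, sensitivity analyses will be performed in the same manner as RMV". Table 6 measures that duration as a cumulative number of days, and SAP 7.2.2 provides no hypothesis tests for additional secondary endpoints.

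**The concern.** The main RMV definition is safe from this problem, because patients who are intubated and ventilated cannot enter. It appears only when high flow is added to the list. A patient who enters on high flow already meets the criterion, and nothing that treatment does can change that patient's result.

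A sensitivity analysis is meant to show whether a finding survives a reasonable change of definition. This one could make a real effect on respiratory support look fragile only because a block of fixed events has been added to both arms.

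**Working it through.** **No figure to reproduce.** The readable text gives no rate, effect or power for RMV or its sensitivity analysis. The conflict between the entry criteria and the ever-use rule needs no assumption; its size does.

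**Inputs**
- ITT size 247 (Protocol synopsis), taken as 124 selinexor and 123 placebo.
- Two-sided alpha 0.05, inferred from the 95% confidence intervals.
- Assumed: h, the share on high flow at entry, equal in both arms, from 10% to 40%.
- Assumed: new use of a listed support in 20% (selinexor) versus 35% (placebo) of patients not on high flow at entry.

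**Formulas**
- Rate as written = h + (1 − h)p, where p is the new-use rate.
- Difference as written = (1 − h) × 15 points.
- Power = Φ[(|d| − 1.96·SE0)/SE1], where d is the difference, SE0 the pooled and SE1 the unpooled standard error. This ignores the CMH strata.

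**Worked case, h = 30%.** Selinexor 0.30 + 0.70 × 0.20 = 44.0%; placebo 0.30 + 0.70 × 0.35 = 54.5%; d = 10.5 points. SE0 = 0.0636 and SE1 = 0.0633, so power = Φ[(0.105 − 0.1247)/0.0633] = Φ(−0.31) = 38%.

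| h | Rates as written | Difference (points) | Automatic events of 247 | Power as written | Power, patients not on high flow at entry |
|---|---|---|---|---|---|
| 0% | 20.0% vs 35.0% | 15.0 | 0 | 75% | 75% |
| 10% | 28.0% vs 41.5% | 13.5 | 25 | 61% | 71% |
| 20% | 36.0% vs 48.0% | 12.0 | 49 | 48% | 66% |
| 30% | 44.0% vs 54.5% | 10.5 | 74 | 38% | 60% |
| 40% | 52.0% vs 61.0% | 9.0 | 99 | 30% | 53% |

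**Other assumed rates.** With 25% versus 40%, power as written is 58%, 47%, 38% and 30% for h of 10% to 40%, against 67%, 62%, 56% and 50% in the limited analysis. SAP 7.1.1 says that about the first 50 ITT patients were randomized 2:1. A 132/115 split on that basis moves power by less than half a percentage point.

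**Step-up rule, all 247 patients kept, h = 30%.** Rate = 0.70p + 0.30e, where e is the escalation rate among patients who entered on high flow.
- e = 30% in both arms: 23.0% vs 33.5%, power 45%.
- e = 0 in both arms: 14.0% vs 24.5%, power 55%.
- e = 20% vs 35%: 20.0% vs 35.0%, power 75%.

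In the first two cases the difference stays at 10.5 points, and the gain over 38% comes from lower variance. The full 15 points return only if treatment also affects escalation among the high-flow patients.

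**Noise.** The standard deviation of the between-arm difference in h is √[h(1 − h)(1/124 + 1/123)], which is 3.8 points at h = 10% and 6.2 points at h = 40%.

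**The case against.** The best defence is that little depends on this analysis. It is a sensitivity analysis of the endpoint that stands third in the SAP's testing order, and it lies outside the formal sequence. Power is a weak yardstick for an analysis with no confirmatory role. The entry share and rates are assumptions, and at a 10% share the loss is modest. All of this stands, and it makes the point a minor one.

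The SAP sentence can also be read literally as restricting the analysis to patients who used one of the supports. Counting them as events is the natural reading for a rate. Restriction would select on a post-randomization variable, so the sentence needs rewriting on either reading.

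Three stronger inferences are tempting, but the documents do not support them.
- **That the duration analysis has the same automatic failures.** Duration is a count of days. A patient who enters on high flow may come off it sooner or later, so that patient remains informative, and no test is planned.
- **That baseline imbalance would be mistaken for a treatment effect.** Under randomization, chance imbalance is part of the sampling variability that the confidence interval and CMH test already cover. It adds noise; it does not bias the result or inflate type I error.
- **That any repair raises power from 38% to 60% at a 30% share.** The 60% belongs only to the analysis that drops patients on high flow at entry. The step-up rule gives about 45% to 75%.

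**Conclusion.** The point holds for the binary RMV sensitivity analysis, as a minor one. On the event reading, every patient on high flow at entry is an event in either arm. The risk difference is multiplied by (1 − h), which is algebra and does not depend on the assumed rates.

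Under the assumed 20% versus 35%, power as written falls from 61% to 30% as h rises from 10% to 40%; limited to patients not on high flow at entry, it falls from 71% to 53%. These figures show scale only, since the true share and rates are not in the documents. A reader might infer that the RMV result itself is compromised. It is not: that definition counts only invasive ventilation or ECMO.

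**What to change.** Rewrite the SAP 7.2.1 sentence as an event definition and state which of two analyses is meant.
1. **Step-up event, all patients kept.** An event is a listed respiratory support newly started after randomization and of a higher type than the support in use at baseline. Use the recorded device type and start date, not the ordinal score: score 3 pools high flow with non-invasive ventilation and would miss a step between them. The SAP should list the order of types.
2. **Limited analysis.** Include only patients not on high flow at baseline.

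These are not interchangeable. Only the first counts a high-flow patient who later needs CPAP/BiPAP, and the two describe different populations. Whichever is chosen, report the number on high flow at baseline per arm.

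For the duration sensitivity analysis in SAP 7.2.2, count only days of support after randomization, and keep the post-randomization high-flow days of patients who entered on high flow.

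The cost is a few lines of SAP text, to be settled before unblinding. No new data are needed, because Protocol 7.3.1 already has the type of respiratory assistance and its start and end dates recorded in the eCRF.
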